Title: Time Limited Eating in Adolescents (Time LEAd): a Pilot Study

NCT Number: NCT03954223

Date of Document: 2/6/2023

Version: 7

PI: [name]

Center for Diabetes, Endocrinology, and Metabolism

Children's Hospital Los Angeles

Los Angeles, CA 90027

Overview of Study Design from Study Protocol:

The aim of this study will be to compare cardiometabolic effects of TLE (8-h eating period/16-h of daily fasting) versus a prolonged eating period (12+ h eating period) in a randomized pilot study with careful control of continuous adherence to prescribed eating window. This study was a prospective, randomized controlled pilot study in 50 adolescents (ages 14–18) with obesity (BMI% ≥ 95th percentile) recruited from clinical programs at Children's Hospital Los Angeles (CHLA). Patients will be randomized to one of three treatment groups for a 12-week intervention: Group 1): Control - Low sugar and carbohydrate educational intervention (LSC, < 5% of total daily calories from sugar/day; < 90 g carbohydrate (CHO)/day) + blinded CGM (used to monitor adherence and glycemic outcomes without real time feedback). Group 2): LSC + TLE (16-h fast/8-h feed for 5 days per week) + blinded CGM.

Table 3: Study Procedures and Measures

Weeks	0	4	12
Consent Completed	x		
Medical history	x		
Demographic Data	x		
CGM Education and equipment	x		
CGM (sensor change every 14 d, 12 w wear time)	x	x	x
Randomized	x		
Primary Outcomes			
Glycemic Control			
Percent Time in Range	x	x	x
Hemoglobin A1c	x	x	
Secondary Outcomes			
Nutrient Data System Recall: 24-hour dietary recall	x	x	
International Physical Activity Questionnaire	x	x	x
Pittsburg Sleep Quality Index and Chronotype Questionnaire	x	x	x
Monitoring for Adverse Events			
Dutch Eating Behavior Questionnaire	x	x	x
Binge Eating Disorder Screen	x	x	x

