
Participants: We recruited 50 adolescents (age 14-18 years at enrollment, all gender expressions), with obesity. Inclusion criteria are: (1) age 14-18 years; (2) Tanner stage III and above; (3) obesity; (4) hemoglobin A1c ≤ 5.7%; (5) participant must be willing and able to adhere to the assessments, visit schedules, and eating/fasting periods; and (6) baseline eating window greater than 10 hours. To limit confounding factors, individuals will be considered ineligible to participate if they meet any of the following exclusion criteria: (1) diagnosis of Prader-Willi Syndrome, brain tumor or hypothalamic obesity; (2) serious intellectual disability; (3) previous diagnosis or subthreshold symptoms of an eating disorder (anorexia nervosa, bulimia nervosa, binge-eating disorder); (4) parent/guardian-reported physical, mental or other inability to participate in the assessments; (5) previous

bariatric surgery; (6) current use of an anti-obesity or other diabetes medication (e.g., phentermine, topiramate, orlistat, glucagon-like-peptide-1 agonist, naltrexone, bupropion, SGLT-2 Inhibitor, or insulin); or (7) current participation in other interventional weight loss studies. A random block stratified randomization scheme was used. Participants were randomized 1:1 via stratified, blocked randomization to ensure the groups were balanced in terms of number of participants and distribution of potential confounding variables including sex and age.

Retention strategies. To foster treatment adherence, participants received weekly calls from the study staff for the duration of the trial. Counseling was conducted by trained research staff. The sessions served three purposes: (1) foster adherence, retention, and accountability; (2) troubleshoot intervention barriers; and (3) monitor safety endpoints. To support participants, the staff will use behavioral techniques, such as stimulus control, goal setting, behavioral contracting, and motivational interviewing. In order to reduce participant burden, if at all possible study procedures will be scheduled to coincide with participants' scheduled clinical visits.

Intervention Arms:

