Components Common to All Study Arms. All participants received two hours of standard nutrition counseling recommended for adolescents living with obesity. No specific caloric restriction was recommended. All participants maintained their usual lifestyle, including physical activity and sleep patterns. Physical activity and sleep recommendations consistent with the American Academy of Pediatrics guidelines for adolescents will be encouraged but not formally prescribed.

Time Limited Eating. The TLE intervention arm involved instructing participants to consume their usual kind and amount of food and beverages (all calories) within a pre-specified 8-hour period, fasting for the remaining 16-hours. They will be free to divide their food and beverage intake into as many meals or snacks as desired during the 8-hour period. We conducted a cross sectional analysis of a cohort of 100 adolescents with obesity and found that most total calories, carbohydrates, and added sugars were consumed between 11 AM and 8 PM.¹³⁶ In addition, in our feasibility trials, most adolescents selected an afternoon/evening eating window for both week days and weekend days, consistent with their shifting sleep/wake cycle and timing of social engagements.¹⁴ Therefore, to align with the normal developmental eating patterns seen in adolescents, we assigned an afternoon/evening TLE approach (consumption of all calories between 12:00 and 20:00 [plus or minus 1 hour] seven days per week). Participants allowed to consume non-caloric beverages (water, tea, coffee) during the fasting period. No energy restriction was required.

Control. Participants assigned to the control arm will be instructed to consume food over a 12-hour or more eating window. They were free to divide their food and beverage intake into as many meals or snacks as desired during the 12-hour period. No energy restriction was required.

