Adherence Monitoring and Intervention Fidelity: To ensure differentiation between the intervention arms all participants recorded the time they start, and finish eating each day and provide their eating logs to the study staff weekly. Each week, study staff will determine the daily eating window for each participant by reviewing the time interval between the first and last caloric intake of the day. These self-reported time windows will be verified by examining the pattern of glucose excursions using the 24-h CGM data. If a participant adheres to meal timing protocol \leq 4 days/week, a follow-up call or videoconference will be scheduled to address challenges, give participants additional encouragement, support, and create a specific plan to promote adherence.

Continuous Glucose Monitor. All participants will be trained to wear a blinded continuous glucose monitor sensor using manufacturer educational materials under the supervision of research staff. Participants will be asked to wear the CGM for the duration of the study. During each study visit, the CGM reader will be connected to the site database to create an individual participant report. Participants will be provided enough sensors to replace the sensor every 14 days. The participants and guardians will be educated on how to use the CGM and receive 1:1 coaching on how to change the sensor, which will be completed either independently or under study team guidance. At each weekly phone meeting, study staff will monitor any challenges related to CGM wear, including participant discomfort, skin adherence, and other issues.

Measurements: The study team will conduct all assessments at week 0, 4, and 12. All data was collected and stored in REDCap.

Statistical Analysis Plan:

Primary Outcome—Feasibility

Compliance with the recommended eating windows was collected from adolescents during the weekly phone calls with the study team. Adolescents were asked to record the time they started and finished eating daily, the number of days they adhered to their prescribed eating schedule, and barriers to adherence. Adolescents were instructed to wear their CGM daily for the duration of the study and to report deviation from the protocol during the phone calls.

Secondary Outcome

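### CGM can contradict a logged fast but cannot verify one, and the primary compliance count makes no use of the contradictions

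*Combined protocol and SAP*

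**What the plan says.** All references are to the combined protocol and SAP.

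- **What the window is.** Adherence Monitoring and Intervention Fidelity has staff derive each daily window by "reviewing the time interval between the first and last caloric intake of the day". Under Intervention Arms, Time Limited Eating (TLE) means "consumption of all calories between 12:00 and 20:00 [plus or minus 1 hour] seven days per week". Both count calories from any source.
- **How it is checked.** The same adherence section states: "These self-reported time windows will be verified by examining the pattern of glucose excursions using the 24-h CGM data". The SAP's Continuous Glucose Monitoring paragraph adds that staff could look each week at excursions falling inside the fasts that participants reported.
- **What is analysed.** Primary Outcome—Feasibility takes compliance from the adolescents during weekly calls. Statistical Analysis summarises adherence as a number of compliant days. CGM enters there only as days worn.
- **What participants eat.** The Overview of Study Design describes a "Low sugar and carbohydrate educational intervention (LSC, < 5% of total daily calories from sugar/day; < 90 g carbohydrate (CHO)/day" limit. The TLE text instead tells participants to "consume their usual kind and amount of food and beverages (all calories) within a pre-specified 8-hour period".
- **Who is enrolled.** Participants must have "hemoglobin A1c ≤ 5.7" per cent at entry, and current diabetes medication is an exclusion.

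The text available gives no excursion threshold, no detection rate, no minimum wear for a day to be judged, and no rule for a disagreement between log and trace. The SAP's CGM paragraph breaks off in mid-sentence at the real-time group, so part of that description may be lost.

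**The concern.** The log and the instrument measure different things. A snack of fat or protein at 22:00 breaches a rule about all calories, yet it may leave no recognisable mark on a glucose trace. Calling the comparison verification treats a quiet trace as proof of fasting, which it is not.

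The evidence that CGM can supply, an excursion where none should be, has no route into the primary outcome. The trial collects a partly independent check on self-report and then analyses self-report alone. The pilot is meant to supply parameters for a larger trial, and the Overview claims careful control of adherence. An unchecked compliance count that readers take to be CGM-verified would give more confidence in adherence, and in the separation of the arms, than the data earn. The follow-up call at four or fewer adherent days a week depends on the same kind of count, and the text does not say whether a CGM contradiction changes it.

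**Working it through.** The plan states no accuracy figure for the check, so there is none to reproduce. The argument is logical, followed by some algebra.

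**Step 1: the two definitions side by side.**

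| | Unit | Source |
|---|---|---|
| Window to be checked | first to last caloric intake | Adherence Monitoring |
| Breach under TLE | any calories outside the window | Time Limited Eating |
| Checking signal | glucose excursion | Adherence Monitoring; SAP, Continuous Glucose Monitoring |

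Carbohydrate-poor intake belongs to the second row and need not appear in the third. That holds whichever diet description applies, because it concerns a single eating occasion.

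**Step 2: what each result can show.** For days logged as compliant, let

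- T = days truly compliant and B = days breached, so the logged count is R = T + B;
- s = probability that a breached day shows a qualifying excursion in the logged fast;
- f = probability that a truly compliant day shows one.

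Planned count: R. Excess over truth = B, whatever s is, because CGM does not enter.

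Expected count after removing contradicted days: R − sB − fT. Excess over truth = (1 − s)B − fT.

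Verification in the ordinary sense needs s = 1. Step 1 shows why s is below 1 for at least some breaches. With f = 0, removal reduces the excess and never overshoots. With f > 0 it can overshoot, when fT exceeds (1 − s)B. The second count is therefore informative, but it is neither an upper nor a lower bound. Days without wear contribute nothing to either term.

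**Step 3: why the contradicted days should not be scaled up.** One might divide the contradicted days by an estimated s. Every input here is assumed and serves only to test that step: 12 weeks × 7 days = 84 days, true compliance 70%, logged compliance 90%, s = 0.10, f = 0.023.

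- T = 0.70 × 84 = 58.8; R = 0.90 × 84 = 75.6; B = 16.8.
- Expected contradicted days = 0.10 × 16.8 + 0.023 × 58.8 = 1.68 + 1.35 = 3.03.
- Divided by the correct s: 3.03 / 0.10 = 30.3 days removed, against 16.8 truly breached. Adherence reads (75.6 − 30.3) / 84 = 54%, not 70%.
- If s is instead estimated as 0.9 from logged meals, which may be easier to detect than snacks: 3.03 / 0.9 = 3.4 days removed. Adherence reads (75.6 − 3.4) / 84 = 86%.

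The correction can miss in either direction. The Overview's five days a week would give 60 days in place of 84, with the same percentages. The five-day and seven-day texts must be reconciled before any day count has a fixed denominator.

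**Step 4: the control arm.** Control participants are told to eat over 12 hours or more. An excursion outside a logged control window means that the true window was longer. That contradicts the log, but not compliance with the instruction. Removing contradicted days thus bears on compliance in the TLE groups, and only on log accuracy in the control arm.

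**The case against.** The strongest reply is that nothing planned is distorted by CGM. The primary outcome is self-report, no CGM-verified rate is an output, and staff already look for excursions in reported fasts, which is the correct direction. On this view the problem is one word in a 50-participant pilot with a convenience sample, supported by daily logs and weekly calls. CGM will also still catch carbohydrate-rich lapses.

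Much of that stands. The check is weak, not useless, and the review of reported fasts is sensible. But the reply also concedes the point: the review is done and its result is left out of the outcome it bears on.

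Three stronger readings are tempting, and the documents do not support them.

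- *Published adherence will be inflated by a given number of points.* No verified figure is planned. The over-reporting rate, the detection rate and the excursion threshold would all have to be assumed.
- *The diet leaves CGM almost blind.* The "< 90 g carbohydrate (CHO)/day" target appears only in the Overview. The Intervention Arms text refers to usual food and standard counselling.
- *The HbA1c criterion shows that excursions will be small.* The documents give no excursion sizes. That inference comes from outside physiology.

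**Conclusion.** The point holds in a limited form. The plan's wording claims more than the check can deliver, because a glucose trace can contradict a log of caloric intake but cannot confirm fasting. The primary count of compliant days is self-reported and ignores contradictions that staff are already placed to see.

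The direction is clear: over-reporting enters the planned outcome undiminished. The size is unknown and cannot be derived from the documents. The conclusion rests on one premise from outside them, that some caloric intake produces no recognisable excursion. It does not depend on the carbohydrate target, on the HbA1c criterion or on any assumed detection rate. This is a cheap improvement to how the feasibility result is reported and read, and it does not threaten the trial's validity.

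**What to change.** 1. In Adherence Monitoring and Intervention Fidelity, replace the claim of verification with a one-directional rule. An excursion in a logged fasting period contradicts the log. A worn day without one is *not contradicted*, and a day without adequate CGM wear is *not assessable*.
2. Fix the excursion definition before it is applied: size, onset time and minimum wear. Judge it by onset, so that a rise continuing after the last logged meal is not counted. State how the one-hour tolerance on the TLE window is handled.
3. In Statistical Analysis, report by arm the self-reported compliant days, the compliant days after contradicted days are removed, and the number of days not assessable. State that the second figure can still overstate adherence because low-carbohydrate intake may be missed, and that false-positive excursions can lower it. For the control arm, add that a contradicted log does not by itself mean a breach of the 12-hour instruction.
4. Do not scale the contradicted days by a detection rate.
5. Reconcile the Overview's carbohydrate target with the usual-food instruction under Time Limited Eating, since the diet affects how much eating CGM can reveal.

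The cost is some SAP wording and one derived variable from logs and CGM files already held. The downside is a second adherence figure that will look less favourable than the first.

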Anthropometrics. All participants received a wireless Bluetooth scale upon consent. Participants' height and weight were collected by the participant and parent/guardian at home with the research coordinator monitoring the measurement collection via a HIPAA compliant virtual platform. Height was measured using a portable wall height indicator tape ruler, accurate to 0.5 cm (Posh Rulers, Quick Medical, Issaquah, WA). Weight was measured on a self-calibrating Etekcity Digital Body Weight Scale, accurate to 0.2 kg (Etekcity, San Diego, CA). Adolescents wore minimal clothing during the height and weight measurements. BMI was calculated as kilograms per meter squared excess percent of the 95th percentile (%BMIp95) was determined utilizing the CDC growth charts.

Continuous Glucose Monitoring

CGM data were downloaded weekly by the study team. CGM data were evaluated continuously over the study period. This data was utilized to compute the following measures: mean, maximum, and minimum glucose levels; standard deviation of glucose; mean amplitude of glycemic excursion; and overall percent of total time spent in euglycemic range (percent time in range = 70–180 mg/dL). All CGM data were housed in Clarity (Dexcom and Dexcom CLARITY are registered trademarks of Dexcom, Inc., San Diego, CA, USA) and the study team had weekly access to assess all glycemic excursions that occurred during the self-reported fasting periods [50–53]. For those in the TLE + real-time

Statistical Analysis

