The study was a pilot trial, thus we opted for a convenient sample size of 50 participants to estimate parameters for a larger, fully powered trial. Analyses were based on the intention to treat (ITT) population using the last observation carried forward. The ITT population was defined as at least two visits (baseline and 1 month). The study was designed as a three-group intervention analysis; however, given that very few adolescents in the TLE+ real-time CGM feedback group looked at their real-time data, we completed a post hoc analysis combining both TLE groups compared to control for all analyses performed. Baseline characteristics (age, sex, race, BMI status, household income) were summarized descriptively across arms for the ITT population using mean and standard deviation (SD) or median and interquartile range as appropriate for the distribution of continuous variables. Categorical variables are described as a frequency and percentage. Continuous variables that are skewed were analyzed in log scale. The differences in demographics, anthropometrics baseline, and eating window distributions among intervention groups were examined using analysis of variance (ANOVA) and Fisher's Exact test. Adherence was operationalized as the number of days adolescents complied with their prescribed eating window, number of days they wore their CGM, and number of weekly phone calls and scheduled research visits they attended, and satisfaction scores were summarized using mean, standard deviation (SD), minimum, and maximum score between TLE and control. The TLE effect on mean change of %BMIp95 between week 0 and week 12 was assessed by using ANOVA. Then, a mixed-effects generalized linear model based on a Gaussian or Gamma distribution as appropriate was used to further assess the TLE effect on change in weight outcome from week 0 to week 12. The mixed-effects generalized linear model based on a Gaussian or Gamma distribution was used as appropriate for the distribution of continuous outcome variables. Whereas a mixed-effects logistic regression model was used for binary clinical outcome variables. In addition, a mixed effects Tobit regression model was used to evaluate the TLE effect on the change in quality- of-life assessment, where the scores are reported in percentages, with no data below 0 or above 100. Then, the non-additive effects of TLE were also examined; specifically, whether the change on clinical outcomes during the study period varied by intervention groups by including the interaction term in the mixed-effect models. In addition, sensitivity analysis was performed to examine whether the weight change observed in the data was influenced by one adolescent who achieved a weight loss of greater than 15% from baseline weight. All results are described in beta estimate, β , percent change, and odds ratio with its associated 95% confidence interval and p-value. The statistical

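### The set called ITT requires a 1-month visit, so feasibility computed on it can be overstated; LOCF is a smaller, secondary problem for the week-12 effect

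*Combined protocol and SAP*

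**What the plan says.** The Statistical Analysis section gives one population rule and one missing-data rule for analyses in general: "Analyses were based on the intention to treat (ITT) population using the last observation carried forward". It then defines the set: "The ITT population was defined as at least two visits (baseline and 1 month".

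The SAP names feasibility as its primary outcome. The Statistical Analysis section measures adherence by days complied with the eating window, days of CGM wear, and the "number of weekly phone calls and scheduled research visits they attended". That sentence names no separate denominator.

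On timing, the Measurements paragraph says "The study team will conduct all assessments at week 0, 4, and 12", and Table 3 places randomisation at week 0. Adherence data accrue more often than visits. Participants "provide their eating logs to the study staff weekly" (Adherence Monitoring and Intervention Fidelity), and the SAP's Continuous Glucose Monitoring paragraph says "CGM data were downloaded weekly by the study team".

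For weight, "The TLE effect on mean change of %BMIp95 between week 0 and week 12 was assessed by using ANOVA", followed by a mixed-effects model. The only sensitivity analysis described concerns one adolescent with a large weight loss. The stated purpose of the 50-person sample is "to estimate parameters for a larger, fully powered trial".

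**The concern.** An intention-to-treat set contains everyone randomised. This one adds a condition met only after randomisation, and the condition (attending a visit) is itself part of the primary outcome. Adolescents who give up in the first month are the strongest evidence against feasibility, and they are the ones removed. Read literally, the rule also drops anyone who misses week 4 but returns at week 12.

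Retention and the mean, SD and minimum of adherence are parameters a pilot hands to the next trial. If they describe only adolescents already retained to 1 month, that trial can be planned too small.

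The second issue is LOCF. After week 4 the only later visit is week 12, so anyone lost in between enters the week-12 comparison with a 4-week value.

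**Working it through.** **No figure of the plan to reproduce.** The sample of 50 is a convenience size, and the documents give no dropout, compliance or SD.

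**What follows from the schedule alone.** With visits at weeks 0, 4 and 12, every member of the set has attended at least 2 of 3 visits (67%). Anyone excluded has attended at most 2, and a baseline-only adolescent 1 (33%). Mean visits in the set therefore cannot be below the mean over all randomised, and is above it once one baseline-only adolescent is excluded. Week-4 attendance in the set is 100%. No dropout model is needed for this.

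**Illustrative size (all assumed).** Of 50 randomised, k leave at day 14 having complied on 50% of days. Of the rest, 10% leave at day 42 and 90% finish at day 84, all 85% compliant while in the study. Fractions of a person are kept as expected values.

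- Days complied: finisher 0.85 × 84 = 71.4; late leaver 0.85 × 42 = 35.7; early leaver 0.5 × 14 = 7.
- Set mean: 0.9 × 71.4 + 0.1 × 35.7 = 67.83. SD: √(0.9 × 0.1) × 35.7 = 10.71.
- All-randomised mean: [(50 − k) × 67.83 + 7k] / 50.
- Visits: set 0.9 × 3 + 0.1 × 2 = 2.90; all randomised 2.90 − (k/50) × 1.90.
- Week-12 attendance: set 90%; all randomised 0.9 × (50 − k)/50.

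| Denominator | Mean days complied | SD | Mean visits | Week-12 attendance |
|---|---|---|---|---|
| Stated set (and all randomised if k = 0) | 67.8 | 10.7 | 2.90 | 90% |
| All randomised, k = 2 | 65.4 | 15.9 | 2.82 | 86% |
| All randomised, k = 5 | 61.7 | 20.9 | 2.71 | 81% |
| All randomised, k = 10 | 55.7 | 26.1 | 2.52 | 72% |

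The minimum falls from 36 days in the set to 7 once any early leaver is counted.

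As a percentage, the gap depends on how days after withdrawal count. At k = 5 it is 67.83/84 = 80.8% against 61.75/84 = 73.5% of 84 days. Over days in study, averaged per person, it is 85% against (45 × 85 + 5 × 50)/50 = 81.5%.

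A simpler bound agrees in direction. If those excluded contribute no adherent days, the set mean is too high by a factor 50/(50 − k): 1.04, 1.11 and 1.25 at k = 2, 5 and 10.

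If retention were taken from within the set, 200 completers would need 200/0.90 = 222.2, so 223 recruits. At the all-randomised figure for k = 5 it is 200/0.81 = 246.9, so 247.

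**LOCF.** Assume the TLE effect accrues linearly, control does not change, and a share d of TLE is lost just after week 4. A leaver carries one third of the week-12 effect, so LOCF estimates 1 − (2/3)d of it.

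- d = 0.10: LOCF gives 0.933. The truth is 1 if leavers would have continued (6.7% too small) or 0.90 if they would have returned to baseline (0.933/0.90 = 1.037, 3.7% too large).
- d = 0.20: LOCF gives 0.867, against 1 (13.3% too small) or 0.80 (0.867/0.80 = 1.083, 8.3% too large).
- No TLE effect, a common 12-week change of 0.5 SD, and loss of 20% against 5%: false difference (0.20 − 0.05) × (2/3) × 0.5 = 0.05 SD. With an assumed 33 against 17 participants the standard error is √(1/33 + 1/17) = 0.30 SD, so the bias is about 0.17 of a standard error.

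**The case against.** The strongest reply is that the plan never says in so many words that feasibility used this set. The set is named again only for baseline characteristics. Step 7 of the implementation steps says recruitment, consent and retention rates were collected continuously to inform future trials, and the first two cannot be computed inside a set defined after randomisation. A wider denominator for retention is therefore plausible. This stands as a limit: the harm is conditional, and the 223 against 247 comparison applies only if retention was taken from within the set. It does not remove the point, because the general rule makes no exception and step 7 gives no denominator.

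Every loss rate above is assumed, and much of the gap in days comes from counting days after withdrawal as non-adherent. Both are true.

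For %BMIp95, an adolescent lost before week 4 has no scheduled post-baseline value, so a modified set is defensible there. That is accepted. Early leavers' eating logs can still exist, because they are submitted weekly. Their CGM data are less certain: one paragraph says weekly downloads, others describe downloads at study visits.

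LOCF affects a secondary outcome in an unpowered pilot, and its bias is small in these examples. Agreed, hence its secondary place. Table 3 lists glycaemic control under primary outcomes while the SAP says feasibility. The two need reconciling, but the SAP's own statement is enough for the concern.

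**Conclusion.** The concern holds. It is certain from the text that the set is attendance-conditional and mislabelled, and that the stated rule, if applied to feasibility, fixes week-4 attendance at 100% and can only raise mean visits. Overstatement of eating-window and CGM days is probable rather than certain; it requires early leavers to have fewer adherent days than those retained.

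The size cannot be fixed from the documents. With 2 to 10 of 50 lost early, the scenario overstates mean days complied by about 2 to 12 and understates the SD; with nobody lost before week 4 the gap is zero. LOCF bias may go either way and is the lesser issue; it too is zero if nobody is lost after week 4. This should be fixed, because the pilot's estimates are meant to feed a larger trial.

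**What to change.** First, define ITT as all randomised, analysed as randomised, and rename the present set modified ITT. Report days complied, CGM days, calls, visits and retention by arm over all randomised, with the numbers lost before week 4 and before week 12. State whether days after withdrawal count as non-adherent or are left out, and show both if in doubt. Keep the present set as a secondary summary of those retained to 1 month.

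Second, make the planned mixed model, fitted to all observed visits (including adolescents who missed week 4 but attended week 12), the main estimate of the week 0 to 12 TLE contrast. Keep LOCF and the ANOVA at most as sensitivity analyses. Add a check for data missing not at random, since difficulty with fasting could plausibly drive dropout; delta-adjusted multiple imputation by arm is one option.

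The cost is SAP wording, a participant-flow count and a re-run on data already held. Feasibility figures may look less favourable, and the mixed-model interval may be wider than the LOCF one.

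### Pooling both TLE arms is a valid main comparison, but it discards the arm-level feasibility estimates that a three-arm pilot could report

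*Combined protocol and SAP*

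**What the plan says.** The Overview of Study Design announces three treatment groups. Item 4 of the implementation steps names them as control, TLE with blinded CGM and TLE with real-time CGM. The Statistical Analysis section agrees: "The study was designed as a three-group intervention analysis". It then explains a departure, "given that very few adolescents in the TLE+ real-time CGM feedback group looked at their real-time data", and states the consequence: "we completed a post hoc analysis combining both TLE groups compared to control for all analyses performed".

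The outcome models that name a contrast name a single one. For the main anthropometric outcome: "The TLE effect on mean change of %BMIp95 between week 0 and week 12 was assessed by using ANOVA". The weight mixed model and the quality-of-life Tobit model are worded the same way. No sentence specifies either TLE arm against control, or real-time against blinded TLE.

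The number of groups is not always clear. The interaction asks "whether the change on clinical outcomes during the study period varied by intervention groups", and the baseline summaries refer to arms or intervention groups without saying how many. The adherence sentence is more definite. Days within the eating window, CGM days, calls and visits attended, and satisfaction scores are "summarized using mean, standard deviation (SD), minimum, and maximum score between TLE and control".

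The SAP's first heading makes feasibility the primary outcome. (Table 3 of the overview lists glycaemic measures under that label; that is a separate matter.) The sample of 50 was chosen "to estimate parameters for a larger, fully powered trial".

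**The concern.** The only stated difference between the two TLE arms is whether the participant could see the glucose data. A team planning the larger trial would want to know whether that feature changed adherence, CGM wear or attendance, and how many participants used it. Randomisation provides that comparison. One pooled TLE column removes it, and the uptake of real-time data, itself a feasibility result, is given only as very few, with no count.

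Three smaller wording matters come from the same three-arm design:

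- The text does not say whether pooling was decided before or after outcomes were reviewed.
- The Participants section gives the allocation as 1:1, which does not literally describe three arms, although its reference to balanced group sizes makes equal arms the likely meaning.
- Item 3 of the implementation steps and the Continuous Glucose Monitor section say that all participants were, or will be, trained on a blinded device, which does not fit the real-time arm in item 4.

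**Working it through.** The plan gives no power, SD, effect size or per-arm number, so there is no figure of its own to reproduce. The question is what pooling gains in precision and what it hides.

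**Inputs.** Total 50 and two-sided 0.05 (Statistical Analysis). Assumed: equal allocation, so 17 control, 17 in one TLE arm and 16 in the other; all 50 analysed; one continuous outcome per participant with common SD = 1. Half-width = t(0.975, df) × SE, in SD units.

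**1. Main contrast, two groups (33 v 17, df 48, t = 2.0106).** SE = √(1/33 + 1/17) = 0.2985; half-width 0.600.

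**2. Main contrast from a three-arm model (df 47, t = 2.0117).** Average of the two TLE means minus control: SE = √(1/17 + 0.25 × (1/17 + 1/16)) = 0.2986; half-width 0.601. If control is the arm of 16, it is 0.610. Keeping three arms costs the main contrast almost nothing.

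**3. Arm-level contrasts from the same model.**
- 17 v 17: SE = √(2/17) = 0.3430; half-width 0.690.
- 17 v 16: SE = √(1/17 + 1/16) = 0.3483; half-width 0.701.

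These cover each TLE arm against control, and real-time against blinded TLE.

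**4. A single arm's mean, as in a feasibility table.** Half-width = t(0.975, n − 1)/√n.
- n = 17: 2.1199/√17 = 0.514.
- n = 16: 2.1314/√16 = 0.533.
- n = 33 (pooled): 2.0369/√33 = 0.355.

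**5. What a pooled mean hides.** If the two TLE means differ by d, the pooled mean lies (16/33)d = 0.48d from the arm of 17 and (17/33)d = 0.52d from the arm of 16. For an assumed d = 0.5 SD that is about 0.25 SD from each; for d = 1.0 SD, about 0.5 SD. The gap itself cannot be seen. No figure in the documents says that the arms differed, so these values of d are illustrative.

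**6. Loss of participants.** The ITT rule requires two visits, so fewer than 50 may be analysed. With an assumed 10% loss (15/15/15, df 42), the average contrast is 0.64 and arm-level contrasts are 0.74. With 20% loss (control 14, TLE 13 and 13, df 37), they are 0.67 and 0.78 to 0.79.

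**The case against.** The best defence is that the plan already does what matters. The overview's aim is to compare TLE with a prolonged eating period, and the Intervention Arms section describes one TLE eating instruction and one control. No objective or hypothesis concerns real-time against blinded CGM. The pooling is disclosed, explained and called post hoc. Low use of the real-time display also makes a large difference between the TLE arms less plausible, and intervals of about 0.7 SD would say little about outcomes.

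Much of this stands. It supports keeping the pooled contrast as the main comparison and treating arm-level results as estimates only. It also limits the request: a three-level arm factor in the mixed logistic, Gamma or Tobit models could be unstable at 16 or 17 per arm, and the precision figures above apply only to a linear model. It does not answer the feasibility point, because a by-arm table needs no model.

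A reader might infer three stronger criticisms. The documents support none of them.

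- *Pooling on behaviour after randomisation biases the result.* Two whole randomised arms are combined. Nobody is selected or reassigned by what they did.
- *Outcomes drove the decision to pool.* The text does not give the timing. Silence is a reason to ask for a sentence, not evidence of influence.
- *Three-arm analyses were never done.* Pooling for all analyses reads most literally as two groups throughout, but it could be an addition to the designed three-group analysis. Likewise, the TLE-against-control phrase in the adherence sentence could attach to satisfaction alone. The text leaves this unclear; it does not establish absence.

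**Conclusion.** The point holds as a worthwhile, inexpensive improvement in reporting. It does not undermine the main comparison. On the natural reading, arm-level adherence, CGM wear, attendance and satisfaction go unreported, although feasibility is the SAP's primary outcome and the data are already collected.

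Under equal arms with all 50 analysed, retaining three arms leaves the main contrast at 0.60 SD and yields arm-level contrasts at 0.69 to 0.70 SD. Each TLE arm's feasibility mean would carry 0.51 to 0.53 SD, against 0.35 SD (0.355 before rounding) for the pooled mean. Dropout widens all of these. The timing, allocation and blinded-CGM matters are wording only and add no weight. The CGM measurement section also breaks off just as it turns to the real-time arm, so text that would settle the last of these may simply not be visible here.

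**What to change.** 1. Tabulate eating-window adherence, CGM wear, call and visit attendance, and satisfaction by the three randomised arms. Add the number in the real-time arm who viewed their data, with its denominator.
2. For %BMIp95 change, and for other continuous outcomes where the model is stable, fit arm as a three-level factor. Report each TLE arm against control, and real-time against blinded TLE, with 95% confidence intervals labelled as estimation only.
3. Keep average TLE against control as the main comparison, with its existing post hoc label. Three-level versions of the binary, Gamma and Tobit models are not needed.
4. Clarify the wording: say when pooling was decided relative to outcome review, give the three-arm allocation ratio actually used, and reconcile the blinded-CGM statements covering all participants with the real-time arm.

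The cost is extra table columns, a few contrasts from data in hand, and some sentences. The drawback is wide arm-level intervals, about 0.7 SD before dropout, which should not be read as tests.
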